8.5.8 TRIAL ENDPOINTS DEFINITION AND ASSESSMENTS

The primary endpoint will be evaluated in a non-inferiority setting, with statistical hypothesis tests formally defined in section 10.

Primary endpoint

The primary endpoint is freedom from MACCE (composite endpoint of all cause death, myocardial infarction, stroke, and valve re-intervention) at one year based on CEC adjudication.

The definitions of each component endpoint are reported in the **Table 4** below, complete definitions can be found in Appendix 4.

Table 4 Definitions of the single endpoint of MACCE

Endpoint	Definition
All cause of death	Total number of deaths regardless of cause (cardiovascular mortality + non cardiovascular mortality)
Myocardial infarction	Myocardial injury as specified in VARC-2 [1]
Stroke	Stroke is defined as an acute episode of focal or global neurological dysfunction caused by the brain, spinal cord, or retinal vascular injury as a result of hemorrhage or infarction. A stroke may be classified as “undetermined” if there is insufficient information to allow the categorization as ischemic or hemorrhagic.
Valve Re-intervention	Any re-intervention, including a transcatheter valve implant, on the implanted aortic valve bioprosthesis after surgical closure of the chest.

Secondary endpoints

1. Surgical time
 - a. Cross clamp time during index procedure
 - b. Cardiopulmonary bypass time during index procedure
2. Normalized Consumption Index and reduced Normalized Consumption Index, including resource consumption items such as (but not limited to):
 - a. Operative room time,
 - b. Duration of ICU/CCU and total hospital stay
 - c. Incidence of specific serious adverse events as defined in Appendix 3
 - d. Blood transfusion(s)
3. Quality of life questionnaire
 - a. At 1 month and 1 year post surgery
4. Intraprocedural and periprocedural serious adverse events regardless of relationship with the device within 72 hours.
5. All valve and procedure relevant serious adverse events as specified in VARC-2 guidelines [1] (Appendix 7)
 - a. Early safety at 30 days
 - b. Clinical efficacy after 30 days
 - c. Time related valve safety: SVD, endocarditis, thrombosis, thromboembolic events (excluding stroke), and bleeding annually up to 5 years
6. Serious device related adverse events up to 5 years
7. Freedom from MACCE at 2, 3, 4 and 5 years of follow up
8. Pacemaker implantation and cause up to 1 year

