10.1.5 SECONDARY ANALYSIS

Each component of the MACCE composite endpoint will be analyzed as proportion of subjects event-free at one year and their 95% C.I. will be reported. In addition, the primary endpoint will be analyzed by means of time-to-event methods (see section 10.1.6) as secondary analysis. For the Cox regression model, the stratification factors (country and surgical approach) and pre-operative variables (including demographic, medical history, and concomitant procedures) will be taken into account. All data collected up to cutoff date will be used for the time-to-event analysis.

Surgical times and Normalized Consumption Index endpoints will be analyzed in a superiority context. A one-sided superiority test will be conducted comparing the treatment and control group at discharge using appropriate regression models to account for stratification factors.

The serious adverse events will be assessed using descriptive statistics. Number of events and number of patients with at least one event will be presented in each group broken down by AE type. Number of events, as well as number and percentage of patients will be tabulated by timing (before / on or after intervention according to VARC-2 definitions). In case of some adverse events occur before intervention, they will be listed separately.

Number of events, as well as number and percentage of patients with at least one event will be reported overall and by treatment group in the Enrolled population, ITT population and Safety population.

Analysis on the secondary endpoint (section 8.5.8) will be detailed and defined in the Statistical Analysis Plan.

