2.3. SAMPLE SIZE CALCULATION

Total sample size for this trial will be adaptively determined through interim analyses. The sample size will be approximately 900, 1050, or 1234 subjects.

The sample size is based on the analysis of primary endpoint (section 10.1) for assessing non-inferiority of Perceval valve arm compared to the control.

Based on CAVALIER experience, propensity score matched studies^{1,4,5,6} and, GARY registry⁷ the freedom from MACCE composite endpoint is expected to be similar for both arms. The original sample size of 1234 patients was based on CAVALIER experience which reported a freedom from MACCE at 1 year equal to 88%. Blinded review of the data for the ongoing current trial (database snapshot December 2017) estimated the pooled one year MACCE-free rate across arms at 91%, showing an overall primary endpoint higher than originally assumed. Due to this reason, 1234 patients may lead to an overpowered study and a smaller sample size may be required to demonstrate study objectives. In

order to adapt the sample size to the real study performance an adaptive design has been included in the study protocol.

Table 1 summarizes the overall operating characteristics of the design over a range of assumptions for the true underlying MACCE-free rate on control ($MACCE_{ctrl}$) and treatment ($MACCE_{PERCEVAL}$). The information provided by the table are:

- Pr(success): it is the proportion of simulated trials achieving success at the final analysis.
 - when the true effect is exactly at the non-inferiority margin (-0.05), it represents the Type I error; otherwise
 - Pr(success) is the power.
- E[N]: it represents the mean sample size across simulated trials, reflecting an average over some trials that stop with N = 900, some at N = 1050, and others at N = 1234.

Table 1 : Overall operating characteristics

True MACCE_{ctrl}	True MACCE_{PERCEVAL}	True Effect	Pr(success)	E[N]
0.88	0.83	-0.05	0.025	1228.7
	0.88	0.00	0.704	1148.9
0.91	0.86	-0.05	0.023	1228.8
	0.91	0.00	0.805	1128.7

Simulations indicate that the adaptive design is able to control the Type I error and Power of the study while looking for the most appropriate sample size. In fact, under the expected assumption of equivalent arms with 91% MACCE-free rate, the trial has approximately 80% power, the type I error rate is controlled to 2.5% one-side and the average sample size is reduced to approximately 1129.

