10.3. PRIMARY ANALYSIS

The primary analysis will calculate the Bayesian posterior probability that the difference [$MACCE_{CONTROL} - MACCE_{PERCEVAL}$] is lower than 0.05 (predetermined non-inferiority margin):

$$\Pr(MACCE_{CONTROL} - MACCE_{PERCEVAL} < 0.05 \mid \text{Data})$$

The null hypothesis will be rejected, and non-inferiority concluded, if the posterior probability exceeds 0.9775 at the final analysis. This threshold was selected based on simulations to control the Type I error rate at 2.5% one-sided (CIP Appendix 8).

The probability $\Pr(MACCE_{CONTROL} - MACCE_{PERCEVAL} < 0.05 \mid \text{Data})$ is calculated on the basis of simulation after the definition of the posterior distribution of p_j according to the following steps:

1. The number of responders X_j is modeled in arm j as $X_j \sim \text{Binomial}(n_j, p_j)$ where n_j is the number of subjects for arm j and p_j is the proportion of subjects that are event-free at one year (response rate);
2. The response rates p_j are then transformed and modeled independently on the log-odds scale. They have a Normal prior distribution:

$$[\theta_j] = \left[\log \left(\frac{p_j}{1 - p_j} \right) \right] \sim N(\theta_0, \sigma_0^2)$$

with $\theta_0 = 1.99$ and $\sigma_0^2 = 3^2$ so that when converted back to the probability scale, this prior is centered at 0.88 (the expected event-free rate for the control arm);

3. One million (1000000) posterior samples for p_j in each arm will be drawn using a standard Markov chain Monte Carlo (MCMC) technique (random walk Metropolis-Hastings algorithm) after discarding the initial set of burnin samples. The calculation of the probability $\Pr(\text{MACCE}_{\text{CONTROL}} - \text{MACCE}_{\text{PERCEVAL}} < 0.05 \mid \text{Data})$ will be done as

$$\frac{\#\text{times} [\text{MACCE}_{\text{CONTROL}} - \text{MACCE}_{\text{PERCEVAL}} < 0.05]}{1000000}$$

In case of test for superiority, the Bayesian posterior probability of superiority

$$\Pr(\text{MACCE}_{\text{CONTROL}} < \text{MACCE}_{\text{PERCEVAL}} \mid \text{Data})$$

will be assessed in the Per Protocol population and will be provided. Superiority will be claimed if the above probability exceeds 0.9775. In order to calculate the probability of superiority, one million (1000000) simulations will be run using the posterior distribution on p_j in each arm, and the calculation of the probability $\Pr(\text{MACCE}_{\text{CONTROL}} < \text{MACCE}_{\text{PERCEVAL}} \mid \text{Data})$ will be done as

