11. SECONDARY EFFICACY ANALYSES

The following secondary efficacy analyses will be performed:

- each component of the primary endpoint will be analyzed as binomial proportion (95% C.I.) of subjects event-free at one year (section 18.12);
- primary endpoint will be analyzed annually as binomial proportion (95% C.I.) of subjects event-free at 1, 2, 3, 4 and 5 years of follow-up (section 18.12);
- The time to the first MACCE will be analyzed using all data collected up to analysis cutoff date (patients may have more that 1-year follow-up):
 - by means of time-to-event methods (see section 5.2)
 - with a Cox regression model, using the stratification factors (country and surgical approach) and pre-operative variables (including demographic, medical history, and concomitant procedures) as covariates. Countries with less than 20 enrolled patients will be pooled. The assumptions of proportionality will also be investigated with a time-dependent exploratory variable, which is defined as $\text{treatment} * \{\log[\text{time to event}]\}$. If the p-value from the Wald Chi-squared statistic for this variable is less than 5% there is

evidence of a departure from the adjusted model assumptions. In case of non-proportional hazards, a Weibull model will be assumed as parametric form of the distribution of survival times. The treatment group will be included in the model as covariate.

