SAE starting date (missing)	In case of missing SAE starting date, the following rule will be applied: 
 1. If missing day: 1st day of the month 2. If missing day and month: 01-JAN 3. If totally missing: Date of surgery SAE starting date cannot be before the surgery date. In that case, SAE starting date will be set as date of surgery.
Deaths	Death is when there is a SAE: 
 - With outcome='FATAL' OR - Leading to death (SAE criteria) The date of death is retrieved from the SAE form (Date of death).
Leak severity	Leak will be classified in: 
 1. none/trace: if "Is there a Paravalvular Leak?" ("Is there a Central Leak?")='No' or severity=' Trace (<1/4+)' 2. mild: if severity=' Mild (1/4+)' 3. moderate/severe: if severity=' Moderate (2/4+)' or severity=' Severe (>= 3/4+)'

Derived variable	Derivation algorithm
Proportion of patient event-free at one year	For each MACCE component: Numerator: #patients who experienced the specific MACCE component within DAY 365 Denominator: #patients who experienced the specific MACCE component within DAY 365 + # patients without the specific event at DAY 365
Proportion of patient MACCE-free at each year	Numerator: #patients who experienced MACCE within DAY 365 (730, 1095, 1460, 1825) Denominator: #patients who experienced MACCE within DAY 365 (730, 1095, 1460, 1825) + # patients without MACCE at DAY 365 (730, 1095, 1460, 1825)
MPG Gradient class	Aortic Mean Pressure Gradient (MPG) class: 
 • MPG \geq 20mmHG • MPG < 20mmHG
Hospitalization time [days]	Discharge – Hospital Admission +1
Ward time [days]	Hospitalization time – ICU time
EQ-VAS	Use as first source of values the “EQ5D02-Your Health Today” variable. If it’s missing, use the “EQ VAS Score” to replace the missing value.
Aortic Mean Pressure Gradient (MPG) with LVOT adjustment	Aortic Mean Pressure Gradient - LVOT Mean Pressure Gradient
Peak Mean Pressure Gradient (MPG) with LVOT adjustment	Aortic Peak Pressure Gradient - LVOT Peak Pressure Gradient

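### Two derivation rows in SAP Table 8 labelled event-free and MACCE-free count the patients who had the event, so they return the complement of the proportion SAP 11 asks for

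*SAP*

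**What the plan says.** SAP 11 schedules two sets of binomial proportions with 95% confidence intervals. For the components: "each component of the primary endpoint will be analyzed as binomial proportion (95% C.I.) of subjects event-free at one year (section 18.12". For the composite: "primary endpoint will be analyzed annually as binomial proportion (95% C.I.) of subjects event-free at 1, 2, 3, 4 and 5 years of follow-up". Both bullets refer to SAP 18.12 for the derivation.

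Table 8 of SAP 18.12 has one row for each. The row for the event-free proportion at one year reads "Numerator: #patients who experienced the specific MACCE component within DAY 365". The row for the MACCE-free proportion at each year reads "Numerator: #patients who experienced MACCE within DAY 365 (730, 1095, 1460, 1825". In both, the denominator is the patients counted in the numerator plus the patients without the event at the same day limit.

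Elsewhere the plan works on the event-free scale:

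- SAP 10.3 says of the modelled rate in each arm that it "is the proportion of subjects that are event-free at one year (response rate".
- Protocol 10.1.5: "Each component of the MACCE composite endpoint will be analyzed as proportion of subjects event-free at one year".
- Protocol 8.5.8, secondary endpoint 7: "Freedom from MACCE at 2, 3, 4 and 5 years of follow up".
- SAP 2.3: the blinded review "estimated the pooled one year MACCE-free rate across arms at 91" per cent.

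**The concern.** The label of each row and its algorithm point in opposite directions. Section 18 of the SAP exists to give the technical detail for implementation, so Table 8 is what a programmer would code from. Nothing in either document says that the result should be subtracted from one.

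The outputs concerned are prescribed ones: the component proportions of Protocol 10.1.5 and freedom from MACCE at years 2 to 5, a listed secondary endpoint. SAP 5.1 has all tables shown by treatment group. If the rows were programmed as written, the arm with more events would carry the higher figure under a MACCE-free heading, and the confidence interval would be mirrored. Any between-arm difference taken under the SAP 18.2 convention (active minus comparator) would change sign.

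**Working it through.** **Which scale the plan uses.** SAP 10.3 centres its prior at 1.99 on the log-odds scale and states that this is 0.88 event-free. Check: 1/(1 + exp(−1.99)) = 0.8797, which rounds to 0.88. The plan's rate scale is thus event-free, and 0.88 is reproduced.

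**What the rows compute.** Let E be the patients with the event by the day limit and F the patients without it.

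- Table 8 as written: E/(E + F)
- Row label and SAP 11: F/(E + F)

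The denominators are identical, so the two values always sum to 1.

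**Size at the documents' own rates.** The 1,000 evaluable patients per line are chosen only for illustration.

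| Event-free rate | Source | E | F | As written | As labelled |
|---|---|---|---|---|---|
| 91% | SAP 2.3, blinded review | 90 | 910 | 90/1000 = 9.0% | 910/1000 = 91.0% |
| 88% | SAP 2.3, original assumption | 120 | 880 | 120/1000 = 12.0% | 880/1000 = 88.0% |
| 86% | SAP Table 1, Perceval at the margin | 140 | 860 | 140/1000 = 14.0% | 860/1000 = 86.0% |

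For the first line the Wald half-width is 1.96 × √(0.91 × 0.09/1000) = 0.018. The interval is 0.072 to 0.108 as written and 0.892 to 0.928 as labelled.

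**Direction between arms.** Take control 0.91 and Perceval 0.86 from SAP Table 1.

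- As labelled: 86.0 − 91.0 = −5.0 points.
- As written: 14.0 − 9.0 = +5.0 points.

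**Whether the text could be an artefact or superseded.** The same inversion stands in two separate, complete rows, and each denominator repeats its numerator phrase, so a broken table does not explain it. The change history in SAP 3.2 lists 18.12 among the sections revised for version 5.0, and the rows stand in the current text.

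**The case against.** The case for treating this as trivial is fair in several respects. The intended direction is clear from the row labels and from every other section. A table showing about 9% MACCE-free, in a trial that assumes 91%, would be noticed. The wrong value is the exact complement of the right one, so no information is lost. SAP 11 also plans a time-to-first-MACCE analysis with Kaplan-Meier estimates, which would show freedom from MACCE the right way round. Finally, SAP 11 schedules proportions with intervals for these rows and no between-arm difference. The ±5-point reversal therefore illustrates direction and is not a planned output; its 0.91/0.86 pair is the simulation scenario at the non-inferiority margin, not an expected result.

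All of that bears on weight. It does not make the rows right. A programmer who noticed the slip would have to depart from the written derivation without any text that authorises it. The reversal of the arms in a by-treatment table also needs no difference to be calculated.

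**Conclusion.** The concern holds. Both rows compute the event proportion under an event-free label, in contradiction of SAP 11, SAP 10.3 and Protocol 10.1.5. Followed literally, they give 9.0% where 91.0% is meant and 12.0% where 88.0% is meant, and they reverse the apparent order of the arms. That conclusion rests only on the wording of the rows; the patient counts above are illustrative and do not affect it.

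The reach is limited to secondary reporting: the component proportions at one year and the yearly MACCE-free proportions, including the descriptive one-year figure. The primary Bayesian analysis is specified separately in SAP 10.3 on the event-free scale. It, the interim rules and the sample size are unaffected. The rows should be corrected before the tables are programmed, but no primary conclusion is at risk.

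**What to change.** In the first row, make the numerator the patients without the specific component event at Day 365. In the second, make it the patients without MACCE at Day 365 (730, 1095, 1460, 1825). Keep both denominators. The rows then return F/(E + F): 910/(90 + 910) = 91.0% in the first example.

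While the rows are open, one sentence could say whether patients who leave event-free before the day limit belong in the denominator. The row wording suggests they do not, while the catch-all *no* in the Table 8 MACCE flags could be read as keeping them. This is a clarification only. It matters mainly for the Safety and mITT populations and for years 2 to 5, since the PP population requires attendance at visits up to one year.

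The cost is two numerator lines in the SAP, plus that sentence if wanted. No protocol amendment, additional data or new analysis is needed.
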